9.3 Sample Size and Accrual

We originally planned to enroll approximately 960 patients into the eligibility phase. From this group, we estimate that 480 participants will report qualifying BPs and will be randomized to one of the eight intervention arms. We anticipate 240 participants will fully complete the 12 month, in person follow up visits.

However, after accruing approximately 400 randomized participants, we noted lower than expected retention at 6 month visits. Therefore, we will adjust the maximum total number of enrollments and randomizations upwards by 50% each. The overall intention is to achieve approximately 240 protocol completers (attendees at 12-month visit). We will continue to monitor accrual and retention in order to achieve this target.

In the work by Collins and others, methods for sample size estimations for factorial design, MOST based interventions, have previously been reported. It is important to note, that the primary hypotheses driven by these designs is not in the pairwise comparisons of each of the interventions, but instead is the overall estimate of the effects of each of the individual intervention components, and their combinations. This smallest standardized effect size of 0.35 corresponds to a BP change of 1 mm Hg and standard deviation of 2.8 mm Hg for each parameter. We believe this is the minimal clinically significant change for each component; and to achieve improvements of 3-4 mm Hg over the course of a year, our chosen regimen for the next phase

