would need a component or combination of components to perform better than an expected 1 mm Hg change. For 80% power to detect the smallest main expected effect of 0.35 based on the Collins method of a 3-factor experiment analyzed using a second order model (i.e. main effects and 2-way interactions), we require 196 participants. Assuming 480 randomized participants, and allowing an additional 50% loss to follow up after the eligibility phase, we expect at least 240 participants, exceeding 80% power with an alpha level of 0.10 (inflated to reduce likelihood of dismissing active components with modest BP reducing effect) – we used the FactorialPower-Plan SAS macro to calculate power. For the secondary analyses, considering an alpha of 0.05 and a baseline proportion attending 2 or more primary care provider visits within one year of 40%, with a total sample size of 240 evenly distributed between the active appointment scheduling and passive appointment, we have 87% power to detect an increase to 60% attending 2 or more visits. The time to event analysis (considering an alpha of 0.05, power of 99%, and 240 participants enrolled over 720 days, followed for 30 days) can detect a change from 20% of participants in the non-facilitated group to 20.4% of participants in the facilitated group. This high power allows ample room to adjust for covariates and loss to follow up. Sample size calculations for secondary outcomes performed with STPLAN (version 4.5).

The challenges of recruiting racial minorities and people with socioeconomic disadvantage for clinical research studies are well documented. Reach Out participant recruitment will be facilitated by several factors: 1) the study is no more than minimal risk; 2) culturally and community sensitive recruitment materials were created using a CBPR approach; 3) enrollment in an urban, safety net ED; and 4) monetary incentives.

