Sample Size: We plan to enroll approximately 960 patients into the eligibility phase. From this group, we estimate that 480 subjects will report qualifying BPs and will be randomized to one of the eight intervention arms. We anticipate 240 subjects will fully complete the 12 month, in person follow up visit. For 80% power to detect the smallest main expected effect of 0.35 based on the Collins method of a 3-factor experiment analyzed using a second order model (i.e. main effects and 2-way interactions), we require 196 subjects. Assuming 480 randomized subjects and allowing an additional 50% loss to follow up after the eligibility phase, we expect at

least 240 subjects, exceeding 80% power with an alpha level of 0.10 (inflated to reduce likelihood of dismissing active components with modest BP reducing effect) – we used the FactorialPowerPlan SAS macro to calculate power. For the secondary analyses, considering an alpha of 0.05 and a baseline proportion attending 2 or more primary care provider visits within one year of 40%, with a total sample size of 240 evenly distributed between the active appointment scheduling and passive appointment, we have 87% power to detect an increase to 60% attending 2 or more visits. The time to event analysis (considering an alpha of 0.05, power of 99%, and 240 subjects enrolled over 720 days, followed for 30 days) can detect a change from 20% of subjects in the non-facilitated group to 20.4% of subjects in the facilitated group.

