2.4. Primary analysis/results

Purpose: Primary results for the intention to treat (ITT) analysis.

Methods/Approach:

Intention to Treat Dataset: all subjects randomized into study and all data observed from each subject regardless of compliance and adherence with the assigned intervention or follow-up.

Primary outcome: Change in systolic BP from baseline (median of three qualifying SBP from eligibility phase) to 12 months. Baseline minus 12 months.

Primary analysis: The primary analysis will fit a linear regression model with the outcome of SBP change and main effect-coded binary predictors of healthy behavior texts (yes vs. no), prompted BP self-monitoring frequency (high vs. low), and primary care provider visit scheduling and transportation (active vs. passive) and the stratification variables. Initial analyses will focus on the main effects. The outcome will be transformed (e.g., log) if necessary.

$$(BL\ BP - 12\ mo\ BP) = \beta_0 + \beta_1\ HBtexts + \beta_2\ HighBPmonitor + \beta_3\ PCPfacilitated + \beta_4\ female + \beta_5\ Age > 65 + \beta_6\ AHT + \beta_7\ Black$$

Where HBtexts= 1 for daily healthy behavior texts and 0 for none; HighBPmonitor=1 if daily BP monitoring and 0 for weekly; PCPfacilitated=1 for provider scheduling and transportation facilitated and 0 for not facilitated; female = 1 for self-reported female, 0 for male; Age>65=1 for Age \geq 65, 0 for 18-64; and AHT=1 for antihypertensives in the past 6 months, 0 for not; Black=1 for Black, 0 for Other

Missing data:

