As a sensitivity analysis, similar to a per protocol analysis, we will assess the effect of using group variables that may change from week to week as opposed to the given randomized treatment variable that stays fixed over the treatment period (intent to treat group). For example, if someone de-escalates from daily to weekly monitoring in a particular week, we can capture this in a longitudinal model by allowing their group variable to change from daily to weekly in that week. This will allow us to connect the BP measurement with the group assignment for that week, thus we will use all BP measurements. Otherwise, the mixed model construction will be the same as detailed in the paragraph above.

(b) Other outcomes (secondary outcomes):

- To evaluate time from ED visit to arrival at first primary care visit (in days)

- Unadjusted survival distributions for receiving provider scheduling and transportation versus not and for all 8 intervention arms will be estimated and plotted by the Kaplan-Meier method and compared using the log-rank test.
- Cox proportional hazards regression model will assess the time from ED visit to arrival at the first primary care visit where all of those who do not have a recorded PCP visit will be censored at the time of last follow-up (last communication/text) or 12 months. The main predictor of interest for these models is assignment to the active primary care provider scheduling and transportation arm (50% of all subjects randomized in the trial), while adjusting for the assignment into other groups (healthy behavior text messages and prompted BP self-monitoring). We will control for age, sex, previous use of antihypertensives, and race. The interactions of these baseline variables will be assessed. The proportionality assumption will be assessed via Schoenfeld residuals by evidence of a non-zero slope in a generalized linear regression of the scaled residuals by time and goodness of fit will be assessed by the Grambsch-Therneau test.
- To evaluate attendance at two or more primary care visits within 12 months of randomization.

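### The time-to-event power statement (99% power, 240 participants, 20% versus 20.4%) is wrong in both documents; power for that difference is about 5%

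*Protocol*

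**What the plan says.** Aim 2 has two endpoints: time from ED visit to first primary care visit (Cox model), and attendance at two or more visits within 12 months (logistic regression).

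For the first, Protocol 9.3 assumes alpha 0.05, "power of 99%, and 240 participants enrolled over 720 days, followed for 30 days", and concludes that the analysis "can detect a change from 20% of participants in the non-facilitated group to 20.4% of participants in the facilitated group". It continues: "This high power allows ample room to adjust for covariates and loss to follow up". The Sample Size paragraph in Section 1 of the SAP carries the same inputs and result: "can detect a change from 20% of subjects in the non-facilitated group to 20.4% of subjects in the facilitated group". Neither document gives a hazard ratio, an event count, the sidedness of the test or the time point to which the percentages refer.

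Three other places bear on the inputs:

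- Protocol 9.3 gives 240 as the expected number of 12-month completers out of 480 randomised. After poor 6-month retention it adds that "we will adjust the maximum total number of enrollments and randomizations upwards by 50% each".
- SAP 2.4 defines the intention-to-treat set as "all subjects randomized into study and all data observed from each subject".
- SAP 2.5(b) says that participants with no recorded visit "will be censored at the time of last follow-up (last communication/text) or 12 months".

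**The concern.** A difference of 0.4 percentage points between two groups of 120 is 0.48 of a participant. No test on 240 people can find that with near certainty, so the sentence looked wrong on its face.

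The cost is in interpretation. A reader who trusts the sentence would take a null Cox result as ruling out even a trivial effect of facilitated scheduling on time to first visit. The protocol's assurance about covariates and loss to follow-up depends on the same figure, in a trial that had already recorded lower retention than planned.

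**Working it through.** **Inputs.** From Protocol 9.3 and SAP Section 1: alpha 0.05, taken as two-sided because the sidedness is not stated; N = 240; accrual 720 days; follow-up 30 days; 20% versus 20.4%. Allocation is half and half, so 120 per level. The new maximum randomised is 480 × 1.5 = 720.

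**1. Reproduce a figure the plan gets right.** For the other Aim 2 endpoint, 40% versus 60% with 120 per group, the two-proportion formula gives

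z = (0.20 − 1.960 × √(2 × 0.50 × 0.50/120)) / √((0.24 + 0.24)/120) = (0.20 − 0.1265)/0.0632 = 1.16,

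so power is 87.7%, against 87% stated. The same formula for 20% versus 20.4% gives 5.1%, both tails counted. This checks the two-proportion calculation only; the log-rank calculation follows separately.

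**2. Hazard ratio.** HR = ln(0.796)/ln(0.80) = 1.0225, and ln HR = 0.0222.

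**3. Expected events under each reading of the follow-up.**

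- Thirty days per person: 120 × (0.200 + 0.204) = 48.5.
- Uniform accrual over 720 days, then 30 more days, with exponential times and 20% read as a 30-day rate: daily hazards are −ln(0.80)/30 = 0.00744 and −ln(0.796)/30 = 0.00761. The event probability is 1 − [exp(−30λ) − exp(−750λ)]/(720λ), which is 0.851 and 0.855. Events are 120 × (0.851 + 0.855), or about 205.

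**4. Power.** Φ(½√E × ln HR − 1.960) + Φ(−½√E × ln HR − 1.960):

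| Scenario | Events | Power |
|---|---|---|
| N = 240, 30 days each | 48.5 | 5.1% |
| N = 240, 720 + 30 days | 205 | 5.3% |
| All 240 have a visit | 240 | 5.3% |
| All 480 have a visit | 480 | 5.7% |
| All 720 have a visit | 720 | 6.0% |

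Simulated log-rank tests (20,000 runs per scenario) rejected in 5.1% and 5.5% of runs for the first two rows.

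**5. Events needed for 99% power.** 4 × (1.960 + 2.326)²/0.0222², using the unrounded logarithm, is about 148,900. With 240 events the hazard ratio would have to be 1.74; with 720 events, 1.38.

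**6. Other readings, N = 240.** A one-sided test gives at most 7.0%. Reading the 20% as the proportion still without a visit, placing it at day 1, 30, 365 or 750, or treating 0.20 and 0.204 as hazards, leaves two-sided power between 5.0% and 5.4%.

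**7. What can be detected.** Solve ½√E × ln HR = 1.960 + z(power). For fixed follow-up, E = (N/2)(p₁ + p₂) and HR = ln(1 − p₂)/ln(1 − p₁). The accrual reading uses the event probabilities of step 3. Starting from 20%, at 80% / 99% power:

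| N | 30 days each | 720 + 30 days (30-day rates) |
|---|---|---|
| 240 | 36% / 45% | 28% / 33% |
| 480 | 31% / 37% | 25% / 29% |
| 720 | 29% / 34% | 24% / 27% |

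The most favourable 99% entry is 26.9%, a gap of 6.9 points against the stated 0.4.

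The SAP's actual horizon is 12 months. The documents give no control rate for a first visit by then, so the rates below are assumed. Detectable rate at 80% power with full follow-up:

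| Assumed control rate | N = 240 | N = 480 | N = 720 |
|---|---|---|---|
| 40% | 58% | 53% | 50% |
| 60% | 76% | 72% | 70% |
| 80% | 91% | 88% | 87% |

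Early censoring would raise the detectable rates for 480 and 720.

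**The case against.** The arithmetic is not in dispute. The other side argues consequence and remedy.

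- **Little depends on it.** The sample size comes from the primary endpoint (196 required, 240 expected). The trial is exploratory, has no efficacy or futility stopping rules and does not control multiplicity. No decision rule uses 20.4%. This stands. It limits the point to a wrong statement, not a flaw in design.
- **It may be a slip.** A gap of 20.4 points (20% versus 40.4%) gives 93.6% as two proportions, 94.7% by log-rank with 30 days each, and above 99.9% with 720 + 30 days. None of these is the stated 99%, so the intended figure cannot be recovered from the documents. The STPLAN output, if kept, should be looked at. The printed sentence has to change either way.
- **The replacement figures rest on assumptions.** This is fair. The 720 + 30 day column treats 20% as a 30-day rate with constant hazard, which puts 1 − 0.80^(365/30) = 93% of controls at a visit by 12 months. Protocol 2.1.1 quotes follow-up adherence of 26% to 56%. If 20% were a 12-month rate under the same accrual, N = 240 gives 36% / 45% and N = 720 gives 29% / 34%. Also, a 40% first-visit rate equals the plan's own rate for two or more visits, so that row is a limiting case. None of this brings 0.4 points within reach.
- **240 is a cautious N.** True, and the intention-to-treat definition sits in SAP 2.4, under the primary analysis; extending it to Aim 2 is an inference. The SAP's Cox description does refer to half of all those randomised and censors those without a visit, so the analysed number is probably above 240. That is a reason to state N.
- **The reassurance sentence could survive a corrected figure.** A new one could be written then. The present one rests on a number that is wrong.

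**Conclusion.** The claim is wrong as written in both documents. Power for 20% versus 20.4% with 240 participants is about 5%, essentially the type I error rate, against 99% stated. That conclusion does not depend on sidedness, on how follow-up is read or on what the percentages mean. The size of the difference that can be detected does depend on assumptions: the control rate, its time point, the number analysed and full follow-up. Over 12 months at 80% power, with control rates of 40% to 80% and N of 240 to 720, it is about 7 to 18 points. The error should be corrected. It concerns a secondary endpoint and leaves the primary sample size untouched.

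**What to change.** 1. In Protocol 9.3 and SAP Section 1, delete the 20.4% claim. Replace it with a detectable difference for the log-rank/Cox analysis that states N, follow-up, control rate with its time point, and power. N needs stating because 240 counts expected 12-month completers, whereas the planned analysis censors those without a visit at last contact or 12 months.
2. In Protocol 9.3, delete the sentence on room for covariates and loss to follow-up.

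Possible content for the new sentence, with the control rate marked as assumed: at two-sided alpha 0.05 and 80% power, from 60% with a first visit within 12 months, the detectable rate is 76% with 240 participants, or 72% with 480 fully followed.

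The cost is one sentence replaced in each document and one deleted in the protocol. Endpoint, analysis, sample size and data collection stay as they are. What is given up is the appearance of very high power: the stated detectable difference rises from 0.4 points to something between about 7 and 18.

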9.4 Data Monitoring

The trial does not employ formal efficacy or futility stopping rules. An independent medical monitor (IMM) will be appointed with responsibility to monitor data and oversee participant safety. IMM will be approved by the NIMHD to provide oversight of the trial. The Reach Out IMM will be an expert in the care of hypertension and may either be an emergency medicine physician or a primary care physician. The frequency of IMM meetings will be determined by the IMM, IC, and PI. Given the planned period of data collection we anticipate about 8-10 meetings, in which to advise about study progress and performance, and to make recommendations regarding study continuation and protocol changes.

10 DATA COLLECTION, SITE MONITORING, AND ADVERSE EXPERIENCE REPORTING

10.1 Records to Be Kept

Some data may be abstracted from the medical record into the participant's research chart. Identifying information will be collected for each individual in the study (phone numbers, name, age, address and additional contact information). This will be used to coordinate the outcome assess-

ments and text message tailoring. We will maintain a link between the study dataset and the patient identifiers to monitor for recurrent events and potential pharmacy information. This linkage file will be retained until the end of data analysis.

Limited access, HIPAA compliant databases on secure servers will be utilized for all data storage and collection. Every effort will be made to protect the confidentiality of participants enrolled in this study. HIPAA regulations will be followed. Each patient will be assigned a unique study identification number, which will be used on all data collection forms. All identifying information recorded on paper will be stored in individual research files for each participant and will be kept in a locked file that is accessible only to study staff. All data stored electronically will be maintained in databases stored on a password protected network drive.

10.2 Role of Data Management

A subset of study participant data outcomes will undergo additional review to assess data quality. A second assessor, will review a random subset. Range checks and content validation will be utilized in the database to ensure high quality data entry.

10.3 Quality Assurance

When applicable, source documents will be uploaded for remote verification. Based on the results of the additional review, retraining of the abstractors will occur if issues with accuracy arise.

11 HUMAN PARTICIPANTS

In general, the research team will adhere to the following principles:

- We will protect and safeguard HIPAA defined Protected Health Information.
- We will respect the confidentiality of the medical providers and health care facilities.
- There will not be public disclosure of identifiable medical provider performance.
- There will not be disclosure or publication of identifiable hospital level performance.
- Identities (patient, provider, and hospital) will be coded in research databases with the linkage file being removed after data analysis.

11.1 Risks

11.1.1 Data risks

The main potential risk to patients in this study is breach of confidentiality of medical records and survey responses that could result in psychological distress. The likelihood of this risk is estimated to be rare. The seriousness to the participant is estimated to be low. We have methods in place to prevent this occurrence. Data obtained for participants will be held strictly confidential in locked facilities and password protected computers. Trained abstractors will enter pertinent information into the database using REDCAP or similar secure online database. Each abstractor is restricted to only the data they collect or have a need to access. Reach Out will use a secure, password-protected web-based application to enter necessary contact information. The text messages are within a SSL encrypted web-based application with secure log-ins to access. A DUA is

in process. We have also obtained a Certificate of Confidentiality from the National Institutes of Health. The Certificate can be used to legally refuse to disclose information that may identify a participant.

11.1.2 Vulnerable populations: pregnant women, prisoners, and children

We are not enrolling vulnerable populations (pregnant women, children, and prisoners). Hypertension is a different disease in pregnancy and in childhood. Prisoners will not generally have access to text messaging, a BP monitoring cuff, or appointments with outside primary care physicians and thus they would not be able to participate or benefit from the study interventions.

All patients of childbearing age will be screened for pregnancy at the time of enrollment. For those who may be pregnant, a pregnancy test may be performed in the Emergency Department (ED) as part of their routine medical care. We are performing research procedures and screening patients in the ED who are visiting for a variety of medical problems and cannot mandate that the clinical care teams perform pregnancy tests. However, in the screening and enrollment process, our research staff will ask potential participants if they could be pregnant. If pregnancy testing has not been done by the clinical team, the research team will inform the clinical team that the patient may be pregnant. The research team will not enroll this patient unless there is a negative pregnancy test. The study would not be dangerous for a pregnant woman; however, the results would not be scientifically relevant.

Once enrolled, participants of childbearing age will be instructed to notify the research team if they become pregnant. Additionally, we will ask participants whether they might be pregnant during the research visits. If the research team learns the participant is pregnant at the research visits or is notified at other times during the intervention, the intervention elements would be discontinued, and we will work with their usual medical care provider to help them establish prenatal care. This will be done because hypertension management differs in pregnancy. In general, by the intention to treat principle, we will keep pregnant women in our cohort to monitor and collect outcomes; we will not use the active intervention components.

Enrolled patients may become prisoners while in our study. The study team will not actively screen for this, however if we learn this during the course of participation we will place study procedures on hold while the patient is a prisoner. We may resume their participation after the period of incarceration, assuming the one-year follow up period has not been expended. We will not extend the follow up window in these cases.

While not a traditionally defined vulnerable population, the people of the city of Flint have faced unique challenges recently given the water crisis. The University of Michigan Department of Emergency Medicine has a long-standing relationship with Hurley Medical Center and the city of Flint. Our faculty group has staffed the emergency department there for almost 20 years. We have an active research infrastructure there and work to reduce the burden of substance abuse and violence in this community. We anticipate that the community will be distrustful of government-funded research, and we will be extremely diligent including working with our community advisory board and employing research staff sensitive to diverse populations. In fact, the research assistants will be part of [name] infrastructure at Hurley Medical Center and

thus have extensive experience recruiting and enrolling this patient population and setting. This research proposal involves limited risks to the community and is truly designed to provide methods of getting better access to hypertension treatment, so it should not be controversial.

